10.6 Management of overdose

N/A

10.7 Pre-medication

No pre-medications are required before treatment with flucloxacillin.

10.8 Permitted, Restricted, and Prohibited Medications

Flucloxacillin has interactions with other medicinal products. For medications known to be contraindicated with the IMP, concomitant treatment should adhere to precautions outlined in the SmPC. Investigators should refer to section 4.5 of the SmPC for details of interactions with other drugs.

Participants taking concurrent oral antibiotic treatment (<24 hours after last dose) will be excluded from the trial for purposes of treatment fidelity. All other concomitant medications clinically indicated are permitted.

Any antibiotics, antithrombotics and immunosuppressant medications that the participant is receiving at the time of enrolment or receives during the trial must be recorded, along with:

• Dosage information, including dose and frequency

10.9 Accountability procedures

Local pharmacy personnel and/or recruiting local research team with delegated responsibility will be responsible for ensuring that the trial medications are managed and dispensed to participants as per local standard practice and guidance and in accordance with the current approved protocol. Each participating site is responsible for keeping accurate records of the IMP supplied by completion of the trial IMP accountability and allocation logs. Accountability procedures will be as per the trial IMP Management plan and IMP Handling Manual, which will be signed-off prior to commencement of the trial.

10.10 Compliance

Participants will receive a one-off dose of either flucloxacillin or placebo after informed consent is received, after randomisation and prior to surgery. The research nurse or delegated site staff will confirm participant has received the intervention by recording on the accountability logs and completing the CRF.

11 Trial procedures

Table 2 below summarises the trial procedures, which will be performed at each visit by the PI or those delegated to do so. Individual trial procedures are described in detail below.

Surgical Procedures

Following randomisation, oral flucloxacillin capsules or placebo will be dispensed by the trial team before surgery, and complete accountability logs according to the IMP Handling manual.

We will recommend adherence to the WHO guidelines for reducing SSI for surgical excision and wound closure (53,54):

Standard preparation of the surgeon including surgical scrub/ alcohol gel and sterile gloves ± gown

- Alcoholic chlorhexidine skin preparation, except where this is contraindicated (such as the face or ears,
 or around mucous membranes) where an aqueous solution should be used), or aqueous povidoneiodine if both an alcohol-based solution and chlorhexidine are unsuitable.
- Absorbable or non-absorbable sutures may be used.
- Skin glue should not be applied to the wound.
- Simple (non-active) dressings should be applied post-operatively, with or without steri-strips, except where this is impractical (such as around the eyes, ear or mouth).

We will monitor adherence with WHO guidelines using a post-surgery specific Case Report Form.

Post Surgical Care Procedures

We will standardise wound care advice and all participants will be advised to contact their local recruiting centre if they have any concern about SSI to arrange a face-to-face clinical review. Outcomes will be assessed by HCPs blinded to allocation.

All participants will receive the standard wound care advice that they would normally receive as part of routine NHS standard of care with possible signs and symptoms of SSI explained to them. Participants will also be given clear written and pictorial material (designed in collaboration with our Patient Partners), including what to look for to identify a wound infection. Participants will be reassured that prompt treatment will be available for any participants with SSI. All participants will be given contact details (including out-of-hours where applicable) of their local recruiting centre and will be advised to contact their local recruiting centre if they have any concerns about wound infection or side effects from the antibiotic tablets to arrange a face-to-face review. Financial assistance will be provided towards participant transport costs for the face-to-face review (if required) to support people on low incomes to participate in the trial, in line with recommendations from the NIHR INCLUDE Socioeconomic Disadvantage Framework (55).

We recognise that some participants with symptoms of wound infection may seek medical advice locally from another health care professional e.g., GP, out-of-hours GP, Emergency Department however participants will be given emergency contact details of their local recruiting site and will be asked to contact them if an SSI is suspected. Suspected SSIs will be assessed at local recruiting site and if an SSI is confirmed, participants will be requested to provide a wound swab, and again 7 days later if infection has not responded to treatment, as per CDC criteria (16).

IRAS: 1009425

Follow-up procedures

Participants will be provided with a patient diary to capture their subjective journey through the trial, and record any symptoms of SSI and notes on their general health, to aid in completion of follow-up assessments by the research team.

All participants will be telephoned by the local research team around days 5-10, days 15-20 and at day 30 (+/-7 days) following surgery to ask about any concerns about wound infection or side effects.

Participants will be encouraged to identify a nominated support person (e.g. a family member) to assist them with trial-related activities, such as wound photos and completing questionnaires, which will support the inclusion of digitally excluded populations and participants with cognitive impairment/ impaired capacity.

SSI diagnosis

A structured Case Report Form will be used to standardise SSI diagnosis using the CDC criteria (16).

We will advise adherence to recommended SSI surveillance protocols as specified in "Protocol for the Surveillance of Surgical Site Infection" produced by the UK HSA (17). Should participants develop any symptoms suggestive of infection then they will be asked to contact their local recruiting centre immediately to arrange an in-person assessment using the CDC criteria. The assessment will be undertaken by a member of the research team or clinical investigator who has been trained in the diagnosis of wound infections.

11.1 Assessments

Outcomes will be assessed at baseline, 5-10 days, 15-20 days 30 days and at 3 months post randomisation. Data will be collected by the research nurses either in person or via telephone, email or post, or review of patient records, and entered in electronic format on the EXCISE database.

The baseline assessments will take place before skin surgery.

Baseline Assessments:

All screening and baseline assessments should be performed on the day of randomisation to determine the participant's eligibility. Written informed consent will be obtained before any trial-specific procedures are undertaken.

IRAS: 1009425

The following assessments at the screening and baseline visits are:

- Completion of eligibility checklist form
- Participant informed consent
- Inclusion/ Exclusion criteria
- Demographics
- Contact details

- Full Medical History
- Concurrent medications
- Skin/ lesion examination
- ECOG Performance Status
- Rockwood Clinical Frailty Score
- Adverse events
- Participant QoL EQ-5D-5L Questionnaire
- Trial Treatment

Assessments at 5-10 days:

- Adverse events
- New antibiotics
- SSI telephone assessment with face-to-face wound review if participant/ clinician concern
- Wound swabs if SSI diagnosed
- 'Selfi-wound' photos will be requested

Assessments at 15-20 days:

- Adverse events
- New antibiotics
- SSI telephone assessment with face-to-face wound review if participant/ clinician concern
- · Wound swabs if SSI diagnosed

11.2 Follow-up

Day 30 (+/- 7 days) and 3 month (+/- 7 days) follow ups will be completed by telephone/email/post by the research nurses.

30-day follow-up:

- Adverse events
- New antibiotics
- SSI telephone assessment with face-to-face wound review if patient/clinician concern
- Wound swabs if SSI diagnosed
- Participant QoL EQ-5D-5L Questionnaire and Bluebelle WHQ questionnaire.

IRAS: 1009425

- Time to return to normal work/ activity
- Resource use (related to wound complications including SSI including report of hospital visits/stays)
- Qualitative interviews (optional n=40)

3-month follow-up:

- Participant QoL EQ-5D-5L Questionnaire
- Time to return to normal work/ activity
- Resource use (related to wound complications including SSI including report of hospital visits/stays)

Around three attempts will be made to contact the participant at each follow-up by telephone. If it is not possible to contact participants, the participant's support person (if nominated) may be contacted as an alternative. If all contact attempts are unsuccessful, a questionnaire booklet may be posted to the participants for them to complete and return.

The follow-up period will end 3 months (+/- 7 days) after the last recruited participant has been randomised and initiates medication (at completion of their 3-month follow-up assessment).

GYMRU Caerdydd a'r Fro
NHS
WALES University Health Board Bwrdd Iechyd Prifysgol Caerdydd a'r Fro

	Assessment	Source Data	Data type/Measure	Screening & Baseline	Day 5-10	Day 15-20	Day 30 (+ 7/7)	3 months (+ 7/7)	Responsible for Data Collection	Justification
1	Eligibility Assessment	Screening log, CRF, documented in medical notes	Inclusion /Exclusion criteria	X					Qualified medical professional with delegated responsibilities	Eligibility
2	Informed consent	Consent form, documented in medical notes	Informed consent	х					Qualified medical professional with delegated responsibilities and site research team who are appropriately qualified, experienced and delegated by the PI	Consent
3	Demographics	CRF	- Age - Sex - Gender - Ethnicity	Х					Site research team	Baseline
4	Contact details	CRF	- Contact details (inc. Postcode) - Alternative Contact details - GP Contact details - NHS number	Х					Site research team	Trial Management
5	Medical history	CRF, documented in medical notes	Co-occurring conditions	Х					Participant Reported/ Site research team	Baseline
6	Skin /lesion examination	CRF, documented in medical notes	Skin surgical site	X	(X)	(X)	(X)		Qualified medical professional with delegated responsibilities	Baseline
7	Concurrent/ new medication	CRF, documented in	- Current medication - Antibiotic use	Х	Х	Х	Х	Х	Participant Reported/ Site research team	Baseline and Fidelity of

CYMRU CHARU Caerdydd a'r Fro
NHS WALES University Health Board

	Assessment	Source Data	Data type/Measure	Screening & Baseline	Day 5-10	Day 15-20	Day 30 (+ 7/7)	3 months (+7/7)	Responsible for Data Collection	Justification
		medical notes								intervention
8	Performance status/ Frailty score	CRF	- ECOG Performance Status- Rockwood Clinical FrailtyScore	Х					Participant Reported/ Site research team	Baseline
9	Randomisation	CRF	Randomised medication	Х					Site research team	Randomisation
10	Dispensing of trial drugs	CRF, documented in medical notes	Trial medication	Х					Site research team	Baseline and Fidelity of intervention
11	Adverse event assessment	CRF, documented in medical notes	- SAEs - SARs	X	Х	X	X		Site research team	Pharmacovigilance
12	SSI assessment (telephone)	CRF	Primary outcome		х	х	X		Qualified medical professional with delegated responsibilities and site research team who are appropriately qualified, experienced and delegated by the PI	Primary outcome
13	SSI assessment (face-to-face)	CRF, documented in medical notes	Primary outcome		(X)	(X)	(X)		Qualified medical professional with delegated responsibilities	Primary outcome
14	Wound swab	CRF, documented in medical notes	Antimicrobial resistance analysis - MALDI- Tof - MIC - EUCAST disc diffusion		(X)	(X)	(X)		Qualified medical professional with delegated responsibilities	Secondary outcome
15	Health- related Quality of Life	CRF	- EQ-5D-5L - Time to return to normal activity	Х			X X	X X	Participant reported	Secondary Outcomes
16	Resource use	CRF	- Health economic data - Resource use				Х	X	Participant reported / Site research team	Secondary outcome

Bwrdd lechyd Prifysgol Caerdydd a'r Fro Cardiff and Vale University Health Board

	Assessment	Source Data	Data type/Measure	Screening & Baseline	Day 5-10	Day 15-20	Day 30 (+ 7/7)	3 months (+ 7/7)	Responsible for Data Collection	Justification
17	'Selfi- wound' (requested)	CRF	- Feasibility		Х				Participant reported / Site research team	Secondary outcome
18	Bluebelle WHQ	Questionnaire	- Response rates - Validity				Х		Participant reported	SWAT
19	Qualitative interviews	- Audio recording- Patient diary- Visual timelineelicitation activity	Secondary outcomes				(X)		CTR Qualitative team	Qualitative
20	Withdrawal	Withdrawal	CRF, withdrawal form		(X)	(X)	(X)	(X)	Participant reported / Site research team	Withdrawal

Table 2. Schedule of enrolment, interventions and assessments (Taken from the HRA CTIMP protocol template (2016).

Page **38** of **69**EXCISE Protocol v1.1 20.10.2025 IRAS: 1009425

12 Sample Management

In addition to wound swabs taken for standard clinical care, trial wound swabs will be collected from all participants who develop SSI and attend their local centre for review and will be repeated seven days later if the SSI does not respond to treatment, as per CDC criteria (16). All trial swabs will be sent to a central microbiology laboratory at Public Health Wales for antimicrobial resistance analysis. This will establish the most common bacterial pathogens associated with SSI and determine their susceptibility/ resistance to clinically relevant antibiotics. All trial swabs will be processed according to Standard Microbiological Investigation B11: Investigation of swabs from skin and superficial soft tissue infections (56) as described in section 18.1.

13 Withdrawal & lost to follow-up

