5.4 Primary outcomes measure

To compare the proportion of participants in the oral flucloxacillin group with the no antibiotic (placebo) group diagnosed with Surgical Site Infection within 30 days post-randomisation.

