16.1 Main analysis

Descriptive statistics will be summarised using frequencies and percentages, means and standard deviations, or medians and interquartile ranges, as appropriate. A comprehensive Statistical Analysis Plan will be approved by the Trial Steering Committee and Trial Data Monitoring Committee prior to database lock and commencement of analysis. The findings will be reported according to the Consolidated Standards of Reporting Trials (CONSORT) statement. We will incorporate the estimand framework within our protocol and

statistical analysis plan (57), with the aim of specifying primary and sensitivity estimands and aligning analysis strategies accordingly.

For the primary outcome statistical analysis, we will compare the proportion of participants in each arm who experience an SSI within 30 days of randomisation using logistic regression. The model will adjust for reconstruction method, anatomical site of surgery and recruitment site. This analysis will include all randomised participants regardless of intervention receipt (as we will be using a treatment policy strategy for handling this intercurrent events). We anticipate deaths occurring within the 30-day post-randomisation period being extremely rare but will handle any instances by incorporating them as a poor outcome (composite strategy). Findings will be reported as odds ratios, 95% confidence intervals, and p-values.

Secondary outcomes will be analysed similarly, with linear, Poisson (or negative binomial), and flexible parametric survival models fitted as appropriate.

Missing data and non-adherence patterns will be described. We will explore their extent and mechanisms and apply appropriate statistical methods for handling these (e.g., multiple imputation, complete case analysis, inverse probability of treatment weighting). Adherence patterns will be characterised using the ABC taxonomy (58). Furthermore, when developing the trial protocol, we will use the estimand framework to outline strategies for handling intercurrent events.

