The acceptability, scale structure and validity of WHQ as a diagnostic tool for SSI with closed wounds in our skin surgery cohort will be assessed. The WHQ will be distributed either by post/ email for participants to complete and return (by stamped addressed envelope, included) or in person/ over the telephone with a research nurse 30 days after surgery. Reference diagnoses of whether SSI had occurred since the time of surgery will be determined as the primary outcome of the EXCISE trial. We will register this SWAT protocol with the MRC Trials Methodology Hub Research SWAT repository (72).

Acceptability will be assessed by calculating response rates, structural validity using confirmatory factor analysis, internal consistency by calculating Cronbach's alpha, and criterion validity by comparing estimated SSIs using the WHQ with SSIs defined by the CDC criteria and calculating the area under the receiver operating characteristic curve value. Data obtained through the semi-structured interviews conducted with patient participants as part of the process evaluation will be used to examine the experience of completing the WHQ, understanding and its acceptability for use within this context. In addition, we will conduct an online focus group with a sample of patients (n=12) to explore themes arising from the interviews relevant to completion and acceptability of the WHQ. Skin surgery is usually carried out as an outpatient procedure and so people undergoing skin surgery are discharged home. Remote assessment of SSI in closed wounds following skin surgery is needed for surveillance and research.

Dissemination of the results will be in line with NIHR guidance, and published open-access once results are available, without delaying the results from the main trial.

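### The 30-day SSI outcome has two different start dates, and its last scheduled assessment may take place on day 23, so an SSI in the final week may go unrecorded

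*Protocol*

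**What the plan says.** **Counting from randomisation.** Section 5.4 defines the primary outcome as the proportion "diagnosed with Surgical Site Infection within 30 days post-randomisation". Section 16.1 compares the proportions who "experience an SSI within 30 days of randomisation using logistic regression", and the interim model in section 16.1.1 uses the same window. Section 11.1 schedules the assessments the same way: "Outcomes will be assessed at baseline, 5-10 days, 15-20 days 30 days and at 3 months post randomisation".

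**Counting from surgery.** Section 11 (Follow-up procedures) has the last SSI telephone call "at day 30 (+/-7 days) following surgery to ask about any concerns about wound infection or side effects". Section 13.2 defines loss to follow-up by failure to complete the day-30 follow-up after surgery. Section 18.2 says of the questionnaire sub-study: "Reference diagnoses of whether SSI had occurred since the time of surgery will be determined as the primary outcome of the EXCISE trial".

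**The window.** Section 11.2 reads "Day 30 (+/- 7 days) and 3 month (+/- 7 days) follow ups will be completed by telephone/email/post" and gives no start date for day 30. In the text available, the Table 2 column heading shows only a plus sign before the seven days. Table 2 schedules the telephone and face-to-face SSI assessments up to day 30 and has no entry for either at 3 months.

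**The concern.** Two things do not fit together. First, one binary outcome has two start dates, and the sub-study treats SSI since surgery as identical to an outcome that elsewhere starts at randomisation. Randomisation is required only to precede surgery (sections 9.5.2 and 15.1); no section says that both happen on one day.

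Second, the tolerance on the last contact runs in both directions. A site that follows the protocol exactly may make its final SSI call a week before the outcome period ends. The participant then has follow-up but no scheduled enquiry for the last week. In a logistic regression on a yes/no outcome, silence in that week is likely to be read as no SSI. Under-recording in both arms lowers both observed rates and so the absolute difference on which the trial is powered. A later analysis plan cannot fully recover a week in which nobody asked.

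**Working it through.** **Step 1: length of the gap.** The earliest permitted final contact is day 30 − 7 = 23, which leaves 30 − 23 = 7 days, or 7/30 = 23% of the window, without scheduled SSI assessment. If the call is timed from surgery, the outcome is timed from randomisation, and surgery is k days after randomisation, the call falls on day 23 + k of the outcome window and the gap is 7 − k days. The protocol does not give k.

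**Step 2: does an early contact count as complete?** Section 13.2 classes a participant as lost only if the day-30 follow-up cannot be completed. Its censoring rule applies only to those lost or withdrawn before day 30. A participant reached on day 23, inside the permitted window, is on the natural reading neither.

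**Step 3: reproduce the sample size.** Inputs from section 15.3: p1 = 0.30 (placebo), p2 = 0.15 (a 15-point reduction), two-sided alpha 0.05, power 90%, 15% loss. Mean rate p = 0.225, d = 0.15.

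n per arm = [1.960·√(2p(1−p)) + 1.282·√(p1(1−p1) + p2(1−p2))]² / d²

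= [1.960·√0.34875 + 1.282·√0.3375]² / 0.0225 ≈ 161

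Total 322; 322/0.85 = 379, against 380 stated. The plan's figure reproduces.

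**Step 4: power if some SSIs go unrecorded.** Analysable per arm: 380 × 0.85 / 2 = 161.5. With a fraction f unrecorded in both arms, the rates become 0.30(1−f) and 0.15(1−f), and

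power = Φ{[d·√161.5 − 1.960·√(2p(1−p))] / √(p1(1−p1) + p2(1−p2))}

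| f (assumed) | Observed rates | Difference (points) | Power |
|---|---|---|---|
| 0% | 30.0% / 15.0% | 15.0 | 90.1% |
| 2% | 29.4% / 14.7% | 14.7 | 89.4% |
| 5% | 28.5% / 14.25% | 14.25 | 88.1% |
| 10% | 27.0% / 13.5% | 13.5 | 85.9% |

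**Step 5: where in that range?** The documents give neither the timing of calls nor that of SSI onset. As an illustration, suppose calls are spread evenly over the 15 days from 23 to 37. Then 7/15 = 47% come before day 30, and the mean unobserved time over all participants is (7+6+5+4+3+2+1)/15 = 1.87 days. With SSI onset flat over 30 days and no self-reporting at all, 1.87/30 = 6.2% of SSIs would be lost, giving a power of 87.6%. Self-reporting would reduce the loss; onset concentrated in the last week would increase it.

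**The case against.** The best reply is that the two dates are probably close and that the calls are not the only route to an SSI diagnosis.

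On dates: "All screening and baseline assessments should be performed on the day of randomisation", and section 11.1 lists trial treatment among the baseline items. The drug is a single pre-operative dose. If the randomisation system is down, section 9.5.2 excludes the patient so that surgery is not delayed. All this points to a short interval, although no section states it. A randomisation anchor is also defensible: all randomised participants are analysed, and it exists even if surgery never happens.

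On detection: participants are told to contact the site at once with any symptoms, with no end date. They keep a diary and receive pictorial guidance, and section 11.1 allows review of patient records. The 3-month contact records antibiotic use and SSI-related resource use. These safeguards are real but partial. No assessment against the CDC criteria is scheduled at 3 months, the expected average age is 77, people who lack capacity are included, and section 11 itself recognises that some participants will seek care elsewhere.

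A reader might infer more than the documents support:

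- **Late SSIs are missed.** They may be; the routes above remain open.
- **Each day between randomisation and surgery enlarges the gap.** Step 1 shows the reverse for calls timed from surgery: the gap is 7 − k.
- **Participants have unequal outcome windows.** The window is 30 days for everyone; what varies is the scheduled observation.
- **Section 11.2 counts day 30 from surgery.** It gives no anchor for day 30.
- **The Table 2 heading proves a conflict with the text.** The plus sign may be a ± sign lost in conversion, and the point does not depend on it.

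**Conclusion.** The point holds as an inconsistency in the anchor combined with an assessment window that opens too early. The start of the 30-day period differs between sections, and following the plan can leave up to 7 outcome days without a scheduled SSI assessment while follow-up is, on the natural reading, complete.

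The effect cannot be sized from the documents. For an assumed 2% to 10% of SSIs unrecorded in both arms, power falls from 90.1% to between 89.4% and 85.9%. This is a modest loss, and self-reporting may keep it near the upper end. Because participants, clinicians and assessors are blinded (section 15.2), the loss is expected to be similar in both arms, and the documents give no ground for inferring a bias in favour of either. The change is worth making because it concerns the primary outcome and is cheap.

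**What to change.** 1. Use one anchor in the synopsis, sections 5.4, 11, 11.1, 11.2, 13.2, 16.1, 16.1.1 and 18.2, and Table 2. Surgery is the natural start of SSI risk; if it is chosen, a rule is needed for anyone randomised who never has surgery. If randomisation is kept, state that surgery is on the same day.
2. Require the final SSI contact no earlier than day 30, for example day 30 to 37, and make the text and Table 2 agree.
3. Let the SSI onset date decide whether an event counts, so that an infection starting after day 30 and found at a late call is excluded.

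The cost is a protocol amendment and a narrower contact window: 8 permitted days (30 to 37) in place of 15 (23 to 37), which gives sites less flexibility. No additional scheduled contacts are needed and the sample size does not change.
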